9.5 STUDY SIZE

The sample size was determined on the basis of feasibility criteria. In fact, according to the volume of patients managed by the centres involved in this study, inclusion of 400 subjects (20 patients/center) with the characteristics defined at Inclusion/Exclusion criteria paragraphs is deemed reasonable for the planned enrolment period (8 months). Assuming a drop-out rate ranging from of 5% to 20% (including not evaluable,lost-to follow up and not on treatment patients), effective sample size is expected to range between 320 (drop out=20%) and 380 (drop out=5%).

An evaluation of the possible achievable precision of the estimates was performed considering the primary objective of the study. No data on treatment satisfaction is available about COPD patients specifically, therefore available literature data was used as a reference to evaluate possible scenarios. In particular, literature data about TSQM was found on multiple sclerosis, psoriasis, etc, showing the global satisfaction mean score ranging from 54.4 to 79.7 (17,18)].

Table 2 shows the 95% confidence interval half-width and standard error (SE) of the expected mean of global satisfaction score under different sample sizes.

| | | | | |
|------------------------------------|-------------|-------|-------------|-------|
| Expected Mean (SD) | 54.4 (21.4) | | 79.7 (16.6) | |
| Sample Size | 380 | 320 | 380 | 320 |
| 95% confidence interval half width | 2.152 | 2.345 | 1.669 | 1.819 |
| Standard error (SE) | 1.098 | 1.196 | 0.852 | 0.928 |

Table 2. 95% confidence interval (CI) half-width and standard error (SE) of the expected mean assuming N=380/320 evaluable patients [19]

In all considered scenarios the relative error of the estimate (CI half-width/expected mean) is lower than 30%. The lower the sample size and the higher the standard deviation, the lower the estimate precision.

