2 DEFINITION OF EVALUABLE PATIENTS

2.1 Patients evaluable at enrolment (FULL ANALYSIS SET)

All enrolled patients meeting the following inclusion / exclusion / other criteria listed in the present paragraph will be considered evaluable at enrollment (Full analysis set) (i.e. COPD patients aged ≥ 40 years, with stable pharmacological treatment for COPD and no exacerbations for at least 3 months, who signed informed consent and privacy form, with at least one Treatment Satisfaction Questionnaire for Medication (TSQM-9) domain score calculated at enrollment visit):

Inclusion criteria

Criterion 1: Patients aged ≥ 40 years

- Question "1. Is the patient aged ≥ 40 years?" = "Yes" [\[F01_INC_EXC_CRITERIA.CI_1\]](#) AND
- Inclusion criterion "1. Patients aged ≥ 40 years?" not checked in the PROTOCOL DEVIATION FORM [\[F24_PROTOCOL_DEVIATION_FORM.PD_CI_1\]](#) AND
- Age at enrollment visit (years) ≥ 40 [\[_PatientInfo.Age\]](#)

Criterion 2: Patients must have a documented diagnosis of chronic obstructive pulmonary disease (COPD)

- Question "2. Has the patient a documented diagnosis of chronic obstructive pulmonary disease (COPD)?" = "Yes" [\[F01_INC_EXC_CRITERIA.CI_2\]](#) AND
- Inclusion criterion "2. Patients must have a documented diagnosis of chronic obstructive pulmonary disease (COPD)" not checked in the PROTOCOL DEVIATION FORM [\[F24_PROTOCOL_DEVIATION_FORM.PD_CI_2\]](#) AND
- Date of COPD diagnosis (mm/yyyy) not missing [\[F04_COPD_MEDICAL_HISTORY.MH_Date_diagnosis\]](#)

Criterion 3: Patients with no exacerbations in the last 3 months

- Question "3. Patient without any exacerbation in the last 3 months" = "Yes" [\[F01_INC_EXC_CRITERIA.QUESTION_3.CI_3\]](#) AND
- Inclusion criterion "3. Patients with no exacerbations in the last 3 months" not checked in the PROTOCOL DEVIATION FORM [\[F24_PROTOCOL_DEVIATION_FORM.PD_CI_3\]](#) AND
- Onset dates at each follow-up visit (Row 1 to 10) [\[F08_EXACERBATIONS.Ex_exacer_1-10_onset_date\]](#) > Date of enrolment visit (dd/mm/yyyy) [\[_PatientInfo.Date_enrollment\]](#)

Criterion 4: Patients requiring regular treatment according to GOLD guidelines, i.e.: undergoing stable pharmacological treatment for COPD since at least 3 months

- Question "4. Does the patient require a regular treatment according to GOLD guidelines, i.e.: undergoing stable pharmacological treatment for COPD since at least 3 months?" = "Yes" [\[F01_INC_EXC_CRITERIA.CI_4\]](#) AND

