| Patients' satisfaction to COPD medical treatments (by means of the TSQM9) at each study visit | X* | X* | X* |
| Patient disease perception (by means of illness perception questionnaire B-IPQ) at each study visit | X* | X* | X* |
| Patient adherence to COPD treatment (by means of MMAS4) at each study visit | X* | X* | X* |
| Patient health status (by means of CAT questionnaire) at each study visit | X* | X* | X* |
| Measurement of dyspnea (by means of mMRC) at each study visit | X* | X* | X* |
| Patient's COPD awareness (COPD awareness questionnaire) at each study visit | X* | X* | X* |
| Relation between treatment satisfaction and demographic (such as age, gender), clinical (such as number of exacerbations, spirometric parameters) parameters and PROs during a 12-month observation period | | | X |
| Description of health care resources utilization and related cost according to the Italian National Health Service (INHS) during a 12-month observation period. | X | | |
| To assess the correlation between patients' satisfaction and resource utilization during a 12-month observation period | | | X |
| Ongoing pharmacological and non-pharmacological treatments for COPD | X | | |
| Exacerbations occurred during observation period | X | | |

*Patients having PRO score computable at the visit will be considered for this analysis (i.e. PRO filled in at the visit and having a sufficient number of items recorded to allow score computation (PROs computation details are reported in Section 3. "Computed Variables"))).

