- (“Start date of therapy” [F20_COPD PHARMACOLOGICAL THERAPY.START_DATE_THER] not missing AND < “Date of follow up visit” [F19_PATIENT_DISPOSITION.PD_2]) AND
- “End date of therapy” [F20_COPD PHARMACOLOGICAL THERAPY.END_DATE_THER] not missing AND > “Date of follow up visit” [F19_PATIENT_DISPOSITION.PD_2]) OR (“End date of therapy” missing AND “Ongoing at the end of observation?” [F20_COPD PHARMACOLOGICAL THERAPY.ONGOING_THER] = “Yes”).

Drug names will be coded by CDM and grouped according to the categories specified above.

Only therapies for COPD will be considered (i.e. those records with field Therapy for [F20_COPD PHARMACOLOGICAL THERAPY.THERAPY_FOR] = “COPD”), while therapies for COPD exacerbations or for COPD-related adverse events will not be considered.

COPD pharmacological treatments: fixed and non-fixed therapy

Patients with fixed COPD pharmacological treatments are those having at least one record of the COPD PHARMACOLOGICAL THERAPY form with “Is it a fixed dose combination?” [F20_COPD PHARMACOLOGICAL THERAPY.DOSE_2] = “Yes” for therapies ongoing at enrollment (see above).

Patients with non-fixed COPD pharmacological treatments are those having at least one record of the COPD PHARMACOLOGICAL THERAPY form with “Is it a fixed dose combination?” [F20_COPD PHARMACOLOGICAL THERAPY.DOSE_2] = “No” for therapies ongoing at enrollment (see above).

Patients who satisfy both conditions will be defined as **patients receiving both COPD pharmacological fixed and non-fixed therapy** at enrollment.

Data manager will check the congruence between the field “Drug” [F20_COPD PHARMACOLOGICAL THERAPY.DRUG] and the question “Is it a fixed dose combination?”: if any fixed dose drug will be entered in the field “Drug” and the question “Is it a fixed dose combination?” = “No” a query will be sent to the investigator. The vice-versa will be checked as well.

Only therapies for COPD will be considered, while therapies for COPD exacerbations or for COPD-related adverse events will not be considered.

COPD pharmacological treatments: patients switching and not switching treatments

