4.3 Patients' satisfaction for medical treatment (TSQM-9) (primary objective)

Table 10. Patients' satisfaction for medical treatment (TSQM-9 items) at each study visit

The table will provide absolute and relative frequency of patients' answers to TSQM-9 items (see Appendix 8.3) at each study visit.

Percentages will be calculated over the number of patients respectively evaluable at the time point considered, namely at enrollment (i.e. FAS patients), at 6 months (i.e. evaluable patients at 6 months) and at 12 months (i.e. evaluable patients at 12 months).

Table 11. Patients' satisfaction for medical treatment (TSQM-9 subscales) at each study visit

The table will provide the descriptive statistics (mean, median, standard deviation, quartiles, min, max) of the TSQM-9 subscales scores (as defined in "Computed variables" chapter) at each study visit.

Changes from enrollment in TSQM-9 subscales scores (see 'Computed variables' chapter) will be also summarized by visit.

95% confidence intervals limits of the mean will be provided for each estimate (i.e. TSQM-9 subscales scores and changes). Descriptives will be calculated over the number of patients respectively evaluable at the time point considered, namely at enrollment (i.e. FAS patients), at 6 months (i.e. evaluable patients at 6 months) and at 12 months (i.e. evaluable patients at 12 months).

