- Absolute and relative frequency of Patients with oxygen therapy during the observational period (see 'Computed variables' chapter)

Percentages will be computed out of the total number of patients evaluable for the FAS.

Table 31. List of oxygen therapies

List of the following variables:

- Patient ID
- "Date of enrollment visit" [[_PatientInfo.Date_enrollment](#)]
- "Kind of therapy" [[F21_OXYGEN_THERAPY.KIND_OF_THER](#)]
- "Drug" [[F21_OXYGEN_THERAPY.DRUG](#)]
- "Flow (L/min)" [[F21_OXYGEN_THERAPY.FLOW](#)]
- "Hours per day" [[F21_OXYGEN_THERAPY.HOURS](#)]
- "Start date of therapy" [[F21_OXYGEN_THERAPY.START_DATE_NF](#)]
- "Ongoing" [[F21_OXYGEN_THERAPY.ONGOING_NF_THER](#)]
- "End date of therapy" [[F21_OXYGEN_THERAPY.END_DATE_NF](#)]
- "Therapy for" [[F21_OXYGEN_THERAPY.NF_THER_FOR](#)]

Only patients evaluable for the FAS will be considered.

Table 32. Patients receiving fixed/non-fixed dose therapies for COPD at enrollment

The table will provide:

- distribution of patients with COPD pharmacological fixed dose therapy at enrollment (see 'Computed variables' chapter);
- distribution of patients with COPD pharmacological non-fixed dose therapy at enrollment (see 'Computed variables' chapter);
- distribution of patients receiving both COPD pharmacological fixed and non-fixed therapy at enrollment (see 'Computed variables' chapter).

Percentages will be computed out of the total number of patients evaluable for the FAS.

Table 33. COPD pharmacological treatments ongoing at enrollment

The table will provide:

- distribution of COPD pharmacological treatments (classes) ongoing at enrollment (see 'Computed variables' chapter).

Percentages will be computed out of the total number of patients evaluable for the FAS.

Table 34. COPD pharmacological treatments ongoing at 6-month follow-up visit

The table will provide:

- distribution of COPD pharmacological treatments (classes) ongoing at 6-month follow-up visit (see 'Computed variables' chapter)

Percentages will be computed out of the total number of patients evaluable for the FAS.

Table 35. COPD pharmacological treatments ongoing at 12-month follow-up visit

The table will provide:

- distribution of COPD pharmacological treatments (classes) ongoing at 12-month follow-up visit (see 'Computed variables' chapter)

Percentages will be computed out of the total number of patients evaluable for the FAS.

Table 36. Medications for adverse events

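### SAP Tables 34 and 35 divide drug use at the 6- and 12-month visits by the whole enrolment FAS, so patients without the visit pull every class percentage down

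*SAP*

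**What the plan says.** - **What the tables show.** SAP 4.10 describes Table 34 as the "distribution of COPD pharmacological treatments (classes) ongoing at 6-month follow-up visit (see 'Computed variables' chapter"). Table 35 is the 12-month equivalent and Table 33 the enrolment one.
- **Denominator.** All three carry the same sentence: "Percentages will be computed out of the total number of patients evaluable for the FAS". Chart 1 (end of SAP 2.3) agrees. Its row "Ongoing pharmacological and non-pharmacological treatments for COPD | X" is marked in the FAS column, and the 6- and 12-month columns are blank.
- **FAS.** SAP 2.1 requires the eligibility criteria and at least one TSQM-9 "domain score calculated at enrollment visit". Nothing after enrolment is required.
- **Numerator.** SAP 3 gives two conditions for a therapy to be ongoing at a follow-up visit. The first is that the start date is "not missing AND < “Date of follow up visit” [F19_PATIENT_DISPOSITION.PD_2]) AND". The second is either an end date after the visit, or no end date and the therapy flagged as ongoing at the end of observation.
- **Other by-visit tables.** For Table 10 the SAP says "Percentages will be calculated over the number of patients respectively evaluable at the time point considered". Tables 11 to 16 likewise use the patients evaluable at each visit.
- **General rules.** Protocol 9.7 follows patients lost to follow-up only as far as their last available visit. The opening of SAP 4 drops patients with missing data from the analysis of the variable concerned.

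**The concern.** The numerator can contain only patients who had the visit, while the denominator contains everyone in the FAS at enrolment. Loss to follow-up therefore enters the percentage as non-use. Table 33 does not have this problem, because every FAS patient was seen at enrolment. Read in sequence, Tables 33, 34 and 35 would drift downward with no change in anyone's treatment.

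Protocol 9.7 undertakes to describe changes in COPD medication since baseline, and these three tables are the class-by-class view of that. A reader could take attrition for stopping or stepping down. As the two tables are described, a patient who was seen and had stopped all COPD drugs cannot be told apart from one who was not seen.

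**Working it through.** **Inputs.** Planned enrolment is 400 and drop-out 5% to 20% (Protocol 9.5). Denominator, FAS definition and numerator rule are as above. The share of the FAS without a given visit, d, is not stated anywhere.

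**The protocol's own figures.** 400 × (1 − 0.05) = 380 and 400 × (1 − 0.20) = 320, matching the effective sample sizes in Protocol 9.5.

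**The numerator rule.** The second bullet has a closing bracket with no opening one, so two readings are possible.

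- Reading A: start before visit AND (end after visit OR ongoing at end of observation). This follows the two-bullet layout.
- Reading B: (start before visit AND end after visit) OR ongoing at end of observation.

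Under A every counted therapy needs a visit date, so a patient without the visit contributes nothing. Under B a patient without the visit still counts if the therapy is flagged as ongoing. But B would also count as ongoing at month 6 a therapy begun after month 6, so it is unlikely to be intended.

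**Formula under A.** Let N be the FAS size and p the use of a class among patients seen. Users counted = p × N × (1 − d). Dividing by N gives a reported percentage of p × (1 − d). Dividing by the patients seen, N × (1 − d), gives p.

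**Numbers** (assumptions: N = 400, use unchanged, loss unrelated to class):

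| Use among patients seen | d = 5% | d = 10% | d = 20% |
|---|---|---|---|
| 80% | 76.0% | 72.0% | 64.0% |
| 60% | 57.0% | 54.0% | 48.0% |
| 50% | 47.5% | 45.0% | 40.0% |
| 30% | 28.5% | 27.0% | 24.0% |

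For the 60% row: 0.60 × 380 = 228 and 228/400 = 57.0%; 0.60 × 360 = 216 and 216/400 = 54.0%; 0.60 × 320 = 192 and 192/400 = 48.0%.

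To look level with Table 33, real use would have to rise by 1/(1 − d) − 1, which is 5.3%, 11.1% or 25% in relative terms at d = 5%, 10% or 20%.

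**Under B**, if patients not seen use the class at the same rate and their therapy is flagged as ongoing, the d = 20% case gives (0.60 × 320 + 0.60 × 80)/400 = 240/400 = 60%, and the shortfall vanishes.

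**How far the 5–20% applies.** Protocol 9.5 includes not-evaluable and not-on-treatment patients in that range. If m of 400 are lost in this broad sense and k of them never enter the FAS, d is at most (m − k)/(400 − k), which is below m/400 whenever k > 0. Patients who were seen but had stopped treatment are true non-users and belong in the denominator, which lowers d further.

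**The case against.** The strongest reply has five parts.

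- *The FAS is the declared set.* Chart 1 and the other patient-level tables of SAP 4.10 use it. That is consistent, but the other follow-up tables count events over the whole observation period, whereas Tables 34 and 35 report status at a visit that some patients never had.
- *SAP 4 already excludes patients with missing data.* Applied here, it could remove patients without the visit. But the specific sentence for each table names the full FAS, so the SAP holds two competing rules. The table layouts are not visible in the public file, so whether they carry a visit n or a missing row cannot be judged.
- *The brackets are ambiguous.* This stands: on the less likely reading the effect largely disappears. It is a reason to correct the rule, not to leave it.
- *Attrition and change are shown elsewhere.* Table 3 reports withdrawals, and the switcher definition with Tables 45 and 46 handles change at patient level. This limits the harm but does not correct the class percentages.
- *The month-12 drug mix is not meant to be set against satisfaction.* This stands. Protocol 9.7 rules out treatment comparisons of satisfaction and pools all treatments, so no planned analysis suffers from the two denominators differing.

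Three stronger inferences are tempting and not supported. A reader might infer that every class will show a fall; a real rise larger than d/(1 − d) would still show as a rise. A reader might infer that 5–20% of patients will appear untreated; SAP 3 says the classes overlap, so their shortfalls do not add up to a count of patients, and no untreated row is described. A reader might take 5–20% as the size of the error; that range covers more than FAS patients without the visit.

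**Conclusion.** The point holds as a downward pull on every class in Tables 34 and 35, by the factor (1 − d), on the natural reading of the section 3 rule. The size is unknown because d is not stated; 5% to 20% relative is an illustrative upper range, or 3 to 12 percentage points for a class used by 60% of those seen. The pull is equal across classes only if loss is unrelated to class. The tables are descriptive and carry no test, and the primary TSQM-9 summaries use visit-specific denominators and are not touched. It should be corrected before the tables are produced, but it does not threaten the study's main result.

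**What to change.** - In Tables 34 and 35, use as denominator the FAS patients with the 6-month (12-month) visit. Show that n and the number of FAS patients not seen.
- Add a row for patients seen with no COPD drug ongoing, so that true stopping is separated from loss.
- Align the Chart 1 row on ongoing treatments with these visit-specific denominators, keeping the FAS for Table 33.
- In SAP 3, correct the brackets so that the start-date condition applies to both end-date alternatives.

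The cost is a few sentences of SAP text and a changed denominator in two programs; no new data are needed. The n becomes smaller at each visit. This base is not identical to that of Tables 10 to 16, which also require the visit window and a TSQM-9 score (SAP 2.2 and 2.3), so the n must be labelled. Patients seen may also differ from those lost, so a change from Table 33 can still partly reflect who remained.

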4.12 Exacerbations

Table 38. Exacerbations: patients' distribution

This table will provide:

- the distribution of patients by number of exacerbations per patient during observation period (see 'Computed variables' chapter);
- descriptive statistics (mean, median, standard deviation, quartiles, min, max) of number of exacerbations per patient during observation period (see 'Computed variables' chapter);
- the distribution of patients by exacerbation severity [[F08_EXACERBATIONS. Ex_Exacer_1_severity - Ex_Exacer_10_severity](#)];
- the distribution of patients by changes in COPD therapy due to exacerbations (i.e. "Any new therapy or any change to an ongoing one required*?") [[F08_EXACERBATIONS. Ex_Exacer_1_change - Ex_Exacer_10_change](#)].

Percentages will be computed out of the total number of patients evaluable for the FAS.

Table 39. Exacerbations: details

This table will provide:

- the distribution of exacerbations by exacerbation severity [[F08_EXACERBATIONS. Ex_Exacer_1_severity - Ex_Exacer_10_severity](#)];
- the distribution of exacerbations by changes in COPD therapy due to exacerbations (i.e. "Any new therapy or any change to an ongoing one required*?") [[F08_EXACERBATIONS. Ex_Exacer_1_change - Ex_Exacer_10_change](#)].

Percentages will be computed out of the total number of exacerbations occurred during observation period in FAS patients.

4.13 Safety

Table 40. Overall Summary of Adverse Events and Adverse Event Reactions

This table will provide:

- the absolute and relative frequency of patients with at least one adverse event (AE) (see 'Computed variables' chapter),
- the absolute and relative frequency of patients with at least one Serious Adverse Event (SAE) (see 'Computed variables' chapter), and
- the patients distribution by "Seriousness Category" [[F22_AES_AND_ADRS.AE_SERIOUSNESS_CAT](#)], and
- the absolute and relative frequency of patients with at least one Adverse Drug Reaction (ADR) to one of the products marketed by Boheringer Ingelheim (namely: Spiriva Handihaler, Spiriva Respimat, Striverdi Respimat, Spiolto Respimat, Oxivent, Dosberotec, Duovent) (see 'Computed variables' chapter), and
- the patients distribution by "Product" [[F22_AES_AND_ADRS.AE_BI_Product](#)]

over the total number of evaluable patients for the Safety set.

Table 41. Patients' distribution by type of adverse event

This table will provide the patients distribution by type of adverse events (i.e. "AE brief description (in English)" [[F22_AES_AND_ADRS.AE_DSCRPT](#)]).

Percentages will be computed over the total number of evaluable patients for the Safety set.

Table 42. Distribution of type of adverse event: details

This table will provide the frequency of each type of adverse events (i.e. "AE brief description (in English)" [[F22_AES_AND_ADRS.AE_DSCRPT](#)]).

Percentages will be computed over the total number of AEs occurred in the Safety set.

Table 43. List of adverse events

The list of all adverse events occurred in the Safety set will be reported. The following variables will be described:

- Patient ID
- "Date of enrollment visit" [[_PatientInfo.Date_enrollment](#)]
- "AE brief description (in English)" [[F22_AES_AND_ADRS.AE_DSCRPT](#)]
- "Date of onset" [[F22_AES_AND_ADRS.AE_ONSET](#)]
- "Is it ongoing at the end of the study?" [[F22_AES_AND_ADRS.AE_ONGOING](#)]
- "End date" [[F22_AES_AND_ADRS.AE_END_DATE](#)]
- "Is it a serious AE" [[F22_AES_AND_ADRS.AE_1](#)]
- "Seriousness category" [[F22_AES_AND_ADRS.AE_SERIOUSNESS_CAT](#)]
- "Is there a reasonable causal relationship with one of the products marketed by BI?" [[F22_AES_AND_ADRS.AE_2](#)]
- "Product" [[F22_AES_AND_ADRS.AE_BI_PRODUCT](#)]
- "Action taken with BI drug" [[F22_AES_AND_ADRS.AE_ACTION](#)]
- "Therapy for the event" [[F22_AES_AND_ADRS.AE_THERAPY](#)]
- "Outcome of the event" [[F22_AES_AND_ADRS.AE_OUTCOME](#)]

[figure not shown]
Table 44. Pregnancies: patients' distribution

[figure not shown]
This table will provide the patients distribution according to the field "Pregnancy" [[F23_PREGNANCY.PREGNANCY_1](#)] over the total number of evaluable patients for the Safety set.

[figure not shown]
[REDACTED]

[figure not shown]
[REDACTED]

[figure not shown]
[REDACTED]

[figure not shown]

[figure not shown]

[figure not shown]

[figure not shown]

[figure not shown]

[figure not shown]

[figure not shown]

[figure not shown]

[figure not shown]

[figure not shown]

[figure not shown]

[figure not shown]

[figure not shown]

[figure not shown]

[figure not shown]

[figure not shown]

[figure not shown]

[figure not shown]

[figure not shown]

[figure not shown]

[figure not shown]

[figure not shown]

[figure not shown]

[figure not shown]

[figure not shown]

[figure not shown]

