11. MANAGEMENT AND REPORTING OF ADVERSE EVENTS/ADVERSE REACTIONS

11.1 DEFINITIONS OF ADVERSE EVENTS

Adverse event

An adverse event (AE) is defined as any untoward medical occurrence in a patient or clinical investigation subject administered a medicinal product and which does not necessarily have a causal relationship with this treatment. An adverse event can therefore be any unfavourable and unintended sign (e.g. an abnormal laboratory finding), symptom, or disease temporally associated with the use of a medicinal product, whether or not considered related to the medicinal product.

Adverse reaction

An adverse reaction is defined as a response to a medicinal product which is noxious and unintended. Response in this context means that a causal relationship between a medicinal product and an adverse event is at least a reasonable possibility. Adverse reactions may arise from use of the product within or outside the terms of the marketing authorization or from occupational exposure. Conditions of use outside the marketing authorization include off-label use, overdose, misuse, abuse and medication errors.

Serious adverse event

A serious adverse event is defined as any AE which

- results in death,
- is life-threatening,
- requires in-patient hospitalization, or
- prolongation of existing hospitalization,
- results in persistent or significant disability or incapacity, or
- is a congenital anomaly/birth defect

Life-threatening in this context refers to a reaction in which the patient was at risk of death at the time of the reaction; it does not refer to a reaction that hypothetically might have caused death if more severe.

Medical and scientific judgement should be exercised in deciding whether other situations should be considered serious reactions, such as important medical events that might not be immediately life threatening or result in death or hospitalization but might jeopardize the patient or might require intervention to prevent one of the other outcomes listed above. Examples of such events are intensive treatment in an emergency room or at home for allergic bronchospasm, blood dyscrasias or convulsions that do not result in hospitalization or development of dependency or abuse. Any suspected transmission via a medicinal product of an infectious agent is also considered a serious adverse reaction.

Adverse Event of Special Interest (AESI)

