11.2 ADVERSE EVENT AND SERIOUS ADVERSE EVENT COLLECTION AND REPORTING

The investigator shall maintain and keep detailed records of all AEs in their patient files.

Collection of AEs

The study design is of non-interventional nature and the study is conducted within the conditions of the approved marketing authorization. Sufficient data from controlled interventional trials are available to support the evidence on the safety and efficacy of the studied BI drug. For this reason the following AE collection and reporting requirements have been defined.

The following must be collected by the investigator in the (e)CRF from signing the informed consent onwards until the end of the study for the BI product administered for the disease in scope of the study:

- all ADRs (serious and non-serious),
- all AEs with fatal outcome ,
- all pregnancies

All ADRs , including those persisting after study completion must be followed up until they are resolved, have been sufficiently characterized, or no further information can be obtained.

The investigator carefully assesses whether an AE constitutes an ADR using the information below.

Causal relationship of adverse event

The definition of an adverse reaction implies at least a reasonable possibility of a causal relationship between a suspected medicinal product and an adverse event. An adverse reaction, in contrast to an adverse event, is characterized by the fact that a causal relationship between a medicinal product and an occurrence is suspected.

Medical judgment should be used to determine the relationship, considering all relevant factors, including pattern of reaction, temporal relationship, de-challenge or re-challenge, confounding factors such as concomitant medication, concomitant diseases and relevant history.

Arguments that may suggest a **reasonable causal relationship** could be:

- The event is **consistent with the known pharmacology** of the drug
- The event is known to be caused by or **attributed to the drug class**.
- A **plausible time to onset of the event** relative to the time of drug exposure.

- Evidence that the **event is reproducible** when the drug is re-introduced
- **No medically sound alternative etiologies** that could explain the event (e.g. preexisting or concomitant diseases, or co-medications).
- The event is typically **drug-related and infrequent in the general population** not exposed to drugs (e.g. Stevens-Johnson syndrome).

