They will be defined as patients with at least one record in the OXYGEN THERAPY log form with (“Start date of therapy” [F21_OXYGEN_THERAPY.SART_DATE_NF] >= “Date of enrollment visit” [_PatientInfo.Date_enrollment]) OR “Ongoing at the end of observation?” [F21_OXYGEN_THERAPY_ONGOING_NF_THER] = “Yes”.

Patients with adverse events, serious adverse events, and adverse drug reactions

Patients with at least one adverse event (AE) will be those with at least one record in the AEs and ADRs log form with “AE brief description (in English)” [F22_AES_AND_ADRS.AE_DSCRIPT] not missing.

Patients with at least one serious adverse event (SAE) will be those with at least one record in the AEs and ADRs log form with “AE brief description (in English)” not missing AND “Is it a serious AE?” [F22_AES_AND_ADRS.AE_1] = “Yes”.

Patients with at least one adverse drug reaction (ADR) to one of the products marketed by Boheringer Ingelheim (namely: Spiriva Handihaler, Spiriva Respimat, Striverdi Respimat, Spiolto Respimat, Oxivent, Dosberotec, Duorent) will be those with at least one record in the AEs and ADRs log form with “AE brief description (in English)” not missing AND “Is there a reasonable causal relationship with one of the products marketed by Boheringer Ingelheim*?” [F22_AES_AND_ADRS.AE_2] = “Yes”.

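### SAP Table 40 reports AE and SAE percentages from a log that protocol 11.2 does not require to hold all AEs or SAEs

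*SAP*

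**What the plan says.** **Collection.** Protocol 11.2 states: "The following must be collected by the investigator in the (e)CRF from signing the informed consent onwards until the end of the study", and limits this to events "for the BI product administered for the disease in scope of the study". Three items follow: "all ADRs (serious and non-serious"), AEs with a fatal outcome, and pregnancies. The expedited-reporting table in the same section has the same scope. Section 11.2 also asks the investigator to keep records of every AE in the patient files. Protocol Table 1 (section 9.3) has an (S)AE assessment row at Visits 2 and 3 with no limit by product or causality.

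**Definitions.** Protocol 11.1 defines an AE as any untoward occurrence, related or not. It lists the criteria that make an AE serious, one of which reads "requires in-patient hospitalization, or".

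**Analysis.** SAP section 3: "Patients with at least one serious adverse event (SAE) will be those with at least one record in the AEs and ADRs log form", provided that the description is filled in and the seriousness field (AE_1) is Yes. The AE definition is the same without the seriousness condition. Neither carries a causality or product condition; an ADR is the separate case with AE_2 = Yes. Table 40 in SAP 4.13 then gives "the absolute and relative frequency of patients with at least one adverse event (AE") and "the absolute and relative frequency of patients with at least one Serious Adverse Event (SAE"), each "over the total number of evaluable patients for the Safety set". SAP 2.4 defines the Safety set without requiring use of a sponsor product. Tables 41 and 42 tabulate F22 records by event type, and Table 43 is described as listing every AE in the Safety set.

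**The concern.** The row labels promise more than the collection rule delivers. A non-fatal event, serious or not, that is not attributed to a sponsor product need not be entered in the eCRF. For a patient taking only other manufacturers' COPD drugs, 11.2 requires no AE entry, yet that patient stays in the denominator. The study covers any COPD treatment, so such patients are expected.

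Safety is not a study objective. Even so, Table 40 is where a reader will look for the AE and SAE frequency in treated COPD patients. A low SAE percentage could be taken as a finding about the patients when it partly reflects what sites were asked to enter. The same report will also show COPD-related hospital admissions from another form, and the two sets of counts may not agree.

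**Working it through.** The plan states no AE, SAE or admission rate, so there is no figure to reproduce. The check sets the rules side by side.

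**1. Definition, collection and counting**

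| Event | Status under protocol 11.1 | eCRF entry required by 11.2? | Counted in Table 40 |
|---|---|---|---|
| Non-serious ADR to the sponsor's COPD product | AE | Yes | AE and ADR rows |
| Serious ADR to that product | SAE | Yes | AE, SAE and ADR rows |
| Fatal AE in a user, not related | SAE | Yes | AE and SAE rows |
| Non-fatal SAE in a user, not attributed to the product | SAE | No | Only if the site chose to enter it |
| Any AE in a patient not on a sponsor product | AE or SAE | No | Only if entered; the patient remains in the denominator |

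With minimum entry, the AE row holds ADRs plus fatal AEs, and the SAE row holds serious ADRs plus fatal AEs, both in sponsor-product users. With uneven extra entry, the rows add an unknown amount of voluntary reporting.

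**2. A consistency check within the report**

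- The Safety set uses criteria 4, 5, 7, 8 and 9 (SAP 2.4). The FAS uses these and others (SAP 2.1), so every FAS patient is in the Safety set.
- COPD-related admissions are recorded on form F10 whatever the product or causality, and are reported for the FAS in Tables 20-23. A severe exacerbation is defined by hospital admission (SAP section 3).
- If F22 held all SAEs, the Table 40 SAE count could not be lower than the number of FAS patients whose AE led to an in-patient admission, counting each patient once across Tables 20 and 22. Under 11.2 it can be lower.

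**3. Illustration on assumed values**

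The documents give none of these rates. Let N = 380 (the upper effective sample size in protocol 9.5, not the size of the Safety set). Let h be the assumed share of patients with at least one in-patient admission for an AE, and r the assumed share of those who are on F22 anyway, as a serious sponsor-product ADR or a fatal AE. Assume minimum entry and independent patients.

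- Patients with an SAE by definition: N × h. Patients among them not required on F22: N × h × (1 − r).
- With r = 10%: h = 1% gives 3.8 and 3.4; h = 5% gives 19 and 17.1; h = 10% gives 38 and 34.2; h = 20% gives 76 and 68.4.
- With h = 10% and r from 0 to 25%: 38 down to 28.5 not required.
- Chance that no patient is affected: (1 − h(1 − r))^N. At h = 1% this is 0.99^380 = 0.022 for r = 0 and 0.9925^380 = 0.057 for r = 25%. At h = 5% or more, with N from 320 to 400 and r up to 25%, the largest value is 0.9625^320 = 4.9 × 10⁻⁶.

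These figures show how easily some shortfall arises under minimum entry. They do not estimate it.

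**4. Categories that must be reported**

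Protocol 11.2 asks for serious ADRs and fatal AEs within 24 hours. The SAP 4.13 text for Table 40 has no row that combines seriousness with causality. Serious ADRs can therefore be identified only in the Table 43 listing.

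**The case against.** The strongest reply is that 11.2 sets a floor and that F22 may hold more.

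- All AEs must be in patient files, and Table 1 schedules an unrestricted (S)AE assessment. F22 has separate seriousness and causality fields, which a form confined to sponsor-product ADRs would hardly need except for fatal events. The SAP was built on an eCRF version dated after the protocol; that form and its completion instructions are not available. This stands. A reader might infer that sites may record only ADRs, fatal AEs and pregnancies, but the documents do not support that: the limit applies to required eCRF entry and expedited reporting.
- Tables 20-23 use another form and another analysis set, cover COPD-related admissions only and include day-hospital stays. An admission is an SAE only if an AE required it. This also stands. The tables may disagree in their results, but the text of the plan is not self-contradictory on this point.
- Table 40 has a row by seriousness category, and death is a seriousness criterion, so deaths may already be shown. The coded values are not given, so the absence of a fatal category cannot be asserted.
- The table shells of SAP 5.13 are not in the public text and might carry a qualifying footnote. That cannot be held against the plan.
- Any admission rate is assumed. No true SAE percentage can be inferred from the illustration.

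None of this makes the two rows interpretable. The definitions in SAP section 3 and the text of SAP 4.13 carry no restriction, and the unrestricted schedule row shows that the protocol itself needs reconciling.

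**Conclusion.** The point holds. Followed as written, the two documents yield AE and SAE percentages that the required collection cannot support, and Tables 41-42 share the problem by event type. The direction depends on practice: too low if sites enter the minimum, a mixture of complete and voluntary reporting if some enter more. Only confirmation that F22 captured all AEs would remove the concern. The size cannot be computed.

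A reader might go further and say that the percentages are certainly understated. That would require knowing that sites entered no more than the minimum, which the documents do not show.

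**What to change.** 1. Reconcile the collection rule in protocol 11.2 with the (S)AE row of protocol Table 1 and with the SAP's description of Table 43 as complete. State which events F22 was meant to hold and, from the eCRF instructions, what sites were told to enter.
2. Unless F22 is confirmed to have captured all AEs, replace the AE and SAE percentage rows of Table 40 with three rows: sponsor-product ADRs (AE_2 = Yes), serious ADRs (AE_1 = Yes and AE_2 = Yes) and fatal AEs (from AE_OUTCOME, assuming that it codes death).
3. Give the fatal-AE percentage only among patients recorded on a sponsor product in the therapy log F20, because fatal AEs in other patients need not be entered.
4. Restrict Tables 41-42 to these categories. Keep other F22 records in the Table 43 listing, flagged as not systematically collected.
5. Footnote that COPD-related admissions are in Tables 20-23, on a different form and analysis set.

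The cost is SAP wording, derived flags from fields already in F22, and a sponsor-product flag from F20. No new data are needed. The downside is that no overall AE or SAE percentage is reported.
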